Ibrutinib and the combination of idelalisib/rituximab have been approved by EMA and FDA. In addition, venetoclax has been recently approved. For patients with R/R CLL, ibrutinib is a commonly used therapeutic option which is also often feasible in elderly and comorbid patients. Ibrutinib has demonstrated significant efficacy in relapsed CLL with durable remissions, including in patients with del(17p)13.1, with moderate toxicity. Recent data demonstrate even more impressive efficacy in previously untreated patients with CLL. Therefore, ibrutinib has been approved by FDA and EMA in 2016 as a first-line treatment for patients with CLL. The approval is based on data from the randomized, multi-center, open-label Phase 3 RESONATE-2 trial, which evaluated the use of ibrutinib versus chlorambucil in 269 treatment-naïve patients with CLL or SLL aged 65 years or older. Ibrutinib significantly prolonged progression-free survival (median PFS was not reached for ibrutinib vs. 18.9 months for chlorambucil) reducing the risk of progression or death by 84% versus chlorambucil. Ibrutinib was also associated with a significantly higher overall response rate versus chlorambucil (ORR of 86% vs. 35%, respectively) (Burger et al., 2015). In several combination trials, ibrutinib has been administered with therapeutic monoclonal antibodies (e.g., rituximab and ofatumumab), chemotherapy (e.g., FCR and BR), and select targeted immune therapies (e.g., lenalidomide). Combination approaches have generally yielded improved overall response rates (ORRs) in part through earlier resolution of persistent lymphocytosis (Byrd et al., 2014b). Most recent results from a large randomized phase III study showed that the combination of ibrutinib and bendamustine/rituximab (BR) decreases the risk of progression and death remarkably (Chanan-Khan et al., 2015).

The emerging resistance to and off-target side effects of ibrutinib have led to active development of second-generation and more specific BTK inhibitors, such as acalabrutinib (ACP-196), ONO/GS-4059, and BGB-3111. Acalabrutinib, which is more potent and selective than ibrutinib with reduced off-target side effects, has recently demonstrated clinical efficacy in relapsed CLL patients and showed encouraging preliminary results offering a favorable safety profile and high response rates that appear durable also in treatment-naïve patients in Phase 1/2 studies. (Byrd et al., 2016a; Byrd et al., 2016b; Wierda et al., 2016). Currently, a

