5.8.2 Previous Treatment with Ibrutinib and Other BTK Inhibitors

The terminal elimination half-life of ibrutinib is 4 to 6 hours according to FDA Prescribing Information ([Appendix B](#)) and 4 to 13 hours according to the European Summary of Product Characteristics (SmPC; [Appendix B](#)). Other BTK inhibitors are currently in phase I-III clinical development e.g., acalabrutinib (ACP-196; Acerta Pharma/AstraZeneca), CC-292 (AVL-292; Celgene), ONO-4059 (Ono/Gilead Sciences) and BGB-3111 (BeiGene). Acalabrutinib has a short mean half-life of 1 hour (Byrd et al., 2016b). The PK-PD relationship of CC-292 was assessed in healthy donors. After single oral dose of 2 mg/kg plasma concentration peaked within 30-120 minutes and declined to near or below the lower limit of detection within 24 hours post dose (Westlin et al., 2012; Evans et al., 2013). Based on results from a phase I study in patients with non-germinal center B-cell like diffuse large B cell lymphoma (non-GCB DLBCL) (ONO-4059POE001), ONO-4059 has a half-life of approximately 5-7 hours (Dyer et al., 2014). It can thus be assumed that the proposed 5-day washout period will suffice to largely clear ibrutinib and other BTK inhibitors from systemic circulation and also from peripheral compartments.

The half-life of BTK, i.e., the target protein of ibrutinib and other BTK inhibitors, is estimated up to 20 hours (Saffran et al., 1994; Yu et al., 2006; Evans et al., 2013). It can thus be assumed that the pharmacological effect of ibrutinib and other BTK inhibitors, i.e., the inhibition of BTK, will have already ceased after the proposed 5-day washout phase. This is also supported by the finding that free BTK protein levels recovered toward 75% of predose values within approximately 4 days after treatment with CC-292 (Evans et al., 2013).

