7.2.1 Inclusion Criteria

Diagnosis/Trial Population

1. Age ≥ 18 years
2. Chronic lymphocytic leukemia (CLL) or small lymphocytic lymphoma (SLL):
 - a) history of diagnosis of CLL or SLL that meets IWCLL diagnostic criteria ([Appendix C](#))
 - b) histologically confirmed diagnosis of SLL by lymph node biopsy and documented within medical records
 - c) indication for treatment as defined by the IWCLL guidelines ([Appendix D](#))
3. Patients must have both of the following:
 - a) relapsed¹ or refractory² disease while receiving a BTK inhibitor (e.g., ibrutinib) or intolerance of such therapy
 - b) single-agent or combination therapy with a BTK inhibitor for at least one month must be the patient's most recent prior anticancer therapy
 - ¹ relapsed disease is defined as progressive disease in subjects who have previously achieved a PR or CR to most recent BTK inhibitor therapy
 - ² refractory disease is defined as progressive disease in subjects who have previously not achieved a PR or CR to most recent BTK inhibitor therapy, or stable disease as best response after 12 months of receiving the most recent BTK inhibitor therapy
4. Eastern Cooperative Oncology Group (ECOG) performance status of 0 to 2
5. Patients with a past medical history of autologous or allogeneic stem cell transplantation must exhibit full hematological recovery without any evidence or ongoing treatment of active graft versus host disease before enrolment into the study.

Laboratory Values

6. Patients must meet the following laboratory criteria at screening:
 - Adequate bone marrow function as follows:
 - a) absolute neutrophil count (ANC) $\geq 1.0 \times 10^9/L$
 - b) platelet count $\geq 30 \times 10^9/L$ in the absence of clinically significant evidence of bleeding
 - c) **Cohort B only:** hemoglobin ≥ 8.0 g/dL
 - Adequate hepatic and renal function as follows:
 - d) total serum bilirubin $\leq 1.5 \times ULN$ or $\leq 3 \times ULN$ in cases of documented liver involvement by CLL (For patients with Gilbert's disease, serum bilirubin up to $3 \times ULN$ is allowed provided normal direct bilirubin.)
 - e) ALT and AST $\leq 2.5 \times ULN$ or $<3 \times ULN$ in cases of documented liver involvement by CLL

- f) serum creatinine clearance calculated using a standard Cockcroft-Gault formula (Cockcroft & Gault, 1976; see [Appendix E](#)) must be:
- **Cohort A only:** ≥ 30 mL/min
 - **Cohort B only:** ≥ 50 mL/min

Other Inclusion Criteria

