4.4 Baseline and Demographic Characteristics

4.4.1 Demography/Baseline Characteristics

All summaries will be presented overall and by cohort in the FAS and SAF. For categorical variables, the number and percentage of patients with missing data will be provided. Demographic and baseline characteristics will include the following:

- age (both continuous and categorical, i.e., <65 and ≥ 65 , <70 and ≥ 70)
- sex and race
- height and weight
- ECOG and disease staging (see section 4.4.2)

- number of prior systemic treatment lines
- time since first CLL/SLL diagnosis (i.e., the interval between the date of first CLL/SLL diagnosis and the screening visit; reported in months)
- time on BTK inhibitor treatment (months) in the most recent prior therapy line containing a BTK inhibitor (not necessarily the last line before entering COSMOS). The following terms will be considered to find the last BTK-containing therapy line: ‘ibrutinib’, ‘imbruvica’, ‘ACP-196’, ‘acalabrutinib’, ‘CC-292’, ‘AVL-292’, ‘ONO-40-59’, ‘BGB-3111’. The variable will be derived as follows: [(End of treatment date for the BTK inhibitor) – (Treatment start date for the BTK inhibitor) + 1]/30.4375.
- the number of patients with beta-2 microglobulin levels >3mg/L at baseline (3 mg/L corresponds to 254.45 nmol/L).
- the number of patients with:
 - neutrophil count $\leq 1.5 \times 10^9$ cells/L at baseline
 - hemoglobin ≤ 11 g/dL at baseline
 - platelet count $\leq 100 \times 10^9$ platelets/L at baseline

The last three items will be summarized for the FAS only. For the time on BTK inhibitor treatment in the most recent prior therapy line containing a BTK inhibitor the following imputations for missing start and stop dates will be made: If the day of the start or stop date is missing but the month is present the day will be imputed by the 15th of the month. If the month of the start or stop date is missing no imputations will be done and the time on BTK inhibitor will be considered as missing.

The demography and baseline characteristics assessed will also be listed by patient.

Note:

- Weight recorded at all the cycles will be presented in the summary of vital signs;
- Baseline BMI will be calculated as: weight at baseline (kg)/squared height at Cycle 1 Day 1 (m^2).

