4.6 Prior and Concomitant Medications and Therapies

Prior medications and concomitant medications will be summarized by cohort for the SAF and FAS using frequency distributions and percentages by Therapeutic Subgroup (2nd level of the Anatomical Therapeutic Chemical [ATC] classification) and Preferred Name.

The medications will be classified according to the following rules:

- Prior medication: start date < date of start of treatment period and stop date ≤ date of start of treatment period
- Concomitant medication: date of start of treatment period ≤ start date < date of study completion/discontinuation
- Prior and Concomitant Medication: start date < date of start of treatment period and stop date > date of start of treatment period or ongoing

The prior and concomitant medications will be listed by Therapeutic Subgroup (2nd level of the ATC classification) and Preferred Name for each patient.

CLL/SLL-specific prior therapies:

The best response and duration of response to the previous regimens patients received will be listed. Duration of Response (DoR) to previous regimens is defined as time (in months) from date of assessment of initial tumor response (CR or PR/PRL) to date of assessment of tumor progression (PD). A partial completion date of initial response and progression will be handled using the algorithm specified in section 4.14.1 (handling of missing data). Furthermore, the time since the completion of last regimen will be listed. Partial completion dates will be imputed using the algorithm specified in section 4.14.1 (handling of missing data).

The number (%) of patients who received 1, 2, 3, etc. prior regimens will be provided. Descriptive statistics will also be provided for the last regimen patients received prior to study entry and the best response (n, %) and duration of response to last therapy (in months). The reason for discontinuation of prior BTK inhibitor will be listed and summarized. The following terms will be used to identify prior BTK inhibitor therapy:

- ibrutinib and imbruvica
- acalabrutinib and ACP-196
- CC-292 and AVL-292

- ONO-40-59
- BGB-3111

Additionally, listings on CLL/SLL-specific surgeries, radiation, and stem cell transplantations will be presented. The number and proportion of patients who have experienced these procedures will be tabulated.

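### Both SAP term lists for prior BTK inhibitors give one drug as ONO-40-59, which does not match the protocol's ONO-4059 or ONO/GS-4059

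*Protocol*

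**What the plan says.** SAP 4.4.1 defines a baseline variable, "time on BTK inhibitor treatment (months) in the most recent prior therapy line containing a BTK inhibitor". It notes that this need not be the last line before study entry. It then gives the search rule: "The following terms will be considered to find the last BTK-containing therapy line", followed by eight names: `ibrutinib`, `imbruvica`, `ACP-196`, `acalabrutinib`, `CC-292`, `AVL-292`, `ONO-40-59` and `BGB-3111`.

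SAP 4.6 plans a listing and summary of why the prior BTK inhibitor was stopped. It gives the same eight names as bullets after "The following terms will be used to identify prior BTK inhibitor therapy". `ONO-40-59` is a bullet of its own there, so a line break in the PDF is an unlikely explanation.

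SAP 4.3 annotates the swimmers plot with the reason for stopping the BTK inhibitor in the last line that contained one. It does not refer to a term list.

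The protocol names the drug differently. Section 5.8.2 (washout rationale) has "CC-292 (AVL-292; Celgene), ONO-4059 (Ono/Gilead Sciences) and BGB-3111 (BeiGene". Section 4.2 describes second-generation agents "such as acalabrutinib (ACP-196), ONO/GS-4059, and BGB-3111".

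Inclusion criterion 3b (Protocol 7.2.1) admits patients after any BTK inhibitor: "single-agent or combination therapy with a BTK inhibitor for at least one month must be the patient's most recent prior anticancer therapy".

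**The concern.** The list is a working derivation rule. It names some drugs twice (ibrutinib with imbruvica, acalabrutinib with ACP-196, CC-292 with AVL-292), which is mainly useful if names are compared as recorded. For this drug the only entry is misspelt, and the GS-4059 alias shown in Protocol 4.2 is absent.

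A patient whose last line was ONO-4059 is eligible. Under the list as written, that line would not count as a BTK inhibitor line. What is at stake is the description of the feature that defines the trial population: how long patients had been on a BTK inhibitor and why they stopped.

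**Working it through.** **Step 1. Compare the names.** The eight SAP terms were matched, ignoring case, as substrings against each BTK inhibitor name in the protocol. This was repeated with punctuation stripped, and again with `ONO-40-59` replaced by `ONO-4059` and `GS-4059`.

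| Name | SAP terms as written | Punctuation stripped | Corrected terms |
|---|---|---|---|
| ibrutinib, acalabrutinib, ACP-196, CC-292, AVL-292, BGB-3111 | found | found | found |
| ONO-4059 | not found | found | found |
| ONO/GS-4059 | not found | not found | found |
| GS-4059 (alias alone) | not found | not found | found |

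This drug is the only one that fails. Ignoring punctuation recovers one of its names but not the alias.

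**Step 2. Effect on time on BTK inhibitor.** SAP 4.4.1 gives (stop date − start date + 1)/30.4375 months, applied to the most recent line that the terms find. Two invented patients show the two outcomes.

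- Ibrutinib for 730 days, then ONO-4059 for 184 days. SAP terms pick the ibrutinib line: 730/30.4375 = 24.0 months. Corrected terms pick the ONO-4059 line: 184/30.4375 = 6.0 months.
- Chemoimmunotherapy, then ONO-4059 for 184 days. SAP terms find no BTK inhibitor line, so the value is missing. Corrected terms give 6.0 months.

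The durations are illustrative and are not trial data.

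**Step 3. Effect on the discontinuation percentages.** SAP 3.2 plans 10 to about 12 patients per cohort, and SAP 4.14.1 keeps missing values in the denominator. One patient is 1/12 = 8.3% of a cohort of 12, 1/10 = 10.0% of a cohort of 10, and 1/24 = 4.2% of both cohorts pooled. For each affected patient:

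- if the earlier line stopped for the same reason category, the shift is 0 points;
- if the category differs, or no line is found, the true category loses 8.3 points in a cohort of 12, and another category or the missing category gains them.

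**Step 4. Which outputs are exposed.** Choosing the most recent matching line is stated only for time on BTK inhibitor in SAP 4.4.1. SAP 4.6 has the same term list but no rule for choosing among lines. SAP 4.3 asks for the last BTK inhibitor line without saying how it is found. The last two outputs are therefore exposed only if they reuse the same identification. The planned analyses of adverse events, ORR, PK and immunogenicity do not use the variable.

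**The case against.** The case for leaving this alone has four parts.

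**Literal matching is not stated.** The SAP does not say whether the terms are applied to recorded text or to coded names. Protocol 11.2 codes medication with the WHO Drug Dictionary Enhanced, so a coded name or a manual read could recover the line. This stands, and a reader should not infer that such a line is certain to be missed. But neither route is specified for this search.

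**The error would often show itself.** A patient with only ONO-4059 would have no BTK inhibitor line in a trial where every patient should have one, and SAP 4.14.1 reports missing data. Listings 16.2.4.9 and 16.2.4.10 show prior therapy by patient, and SAP 4.20 calls for outputs to look logical and for related outputs to be compared. It would therefore be too strong to infer that the error is invisible. What remains is the older-line case, where a plausible value is printed. Independent programming from the same list could reproduce it, and no targeted reconciliation is planned.

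**Possibly nobody is affected.** The documents give no count. The clinical data that Protocol 5.8.2 cites for this drug come from a phase I study in a different lymphoma. This stands.

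**No endpoint is touched.** SAP 4.1.3 plans no subgroup analyses, SAP 3.1 drops the prognostic-factor objective, and no hypothesis is tested. This stands and limits the importance of the point.

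**Conclusion.** The mismatch is real and appears in both SAP lists. If the terms are matched as written, a prior line with this drug is not recognised, and time on BTK inhibitor comes from an earlier BTK inhibitor line or is missing. The discontinuation-reason summary and the swimmers-plot annotation could be wrong in the same way if they use the same identification.

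The size is small and uncertain. The number of affected patients is undocumented and may be zero. Each one shifts the discontinuation percentages by 0 points or by about 8.3 points in a cohort of 12 (10 points in a cohort of 10).

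Three stronger readings are tempting, and the documents do not support them. All three outputs do not demonstrably follow one rule, because the choice of the most recent line is written only for time on BTK inhibitor. An affected patient does not always move the percentages, because the reason category may be the same on both lines. The trial's safety and response results are not in doubt.

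The correction is still worth making. It is specific, costs almost nothing, and protects the description of the population that the trial was designed for.

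**What to change.** In SAP 4.4.1 and 4.6, replace `ONO-40-59` with `ONO-4059` and add `GS-4059`, which also catches ONO/GS-4059. State whether the terms are applied to recorded or coded drug names, and say that the 4.6 summary and the swimmers plot use the same identified line.

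Add one programmed check: every treated patient has a matched BTK inhibitor line, and that line is the last one before Cycle 1 Day 1, as inclusion criterion 3b requires. Send mismatches to data review and do not let them fall back to an older line, since a mismatch may be either a naming variant or a genuine eligibility deviation. The check would also pick up spelling variants of the other BTK inhibitors.

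The cost is a change of wording in two lists, a sentence on matching and one data check on about 24 patients. No data collection changes.

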5.9 Rationale for Biomarker Assessment

Several prognostic markers have been described that can be used as stratification factors for CLL/SLL therapies. These include del(17p), del(11q), del(13q14), trisomy 12, immunoglobulin heavy-chain variable (IGHV), NOTCH1 and TP53 mutations as well as serum parameters (thymidine kinase, β 2 microglobulin) or CLL cell markers (CD38, ZAP-70). There is increasing evidence from prospective clinical trials that detection of certain chromosomal deletions has prognostic significance in CLL. For example, patients with leukemia cells that have del(17p) and/or TP53 mutations have an inferior prognosis and appear to be resistant to standard chemotherapy regimens (Hallek et al., 2008, Stilgenbauer et al., 2014). The presence of del(17p)/TP53 mutation and complex karyotype may also contribute to the genomic instability in CLL cells, and prior therapies can promote subclonal mutations and refractory disease in patients with CLL.

BTK mutations and clonal evolution may occur and produce ibrutinib resistance. There are recent data reported on acquired ibrutinib resistance and BTK mutation (C481S) and phospholipase C γ 2 mutation in patients with CLL who progressed on ibrutinib therapy (Woyach et al., 2014b). Further, expression levels of BCL2/BH3 protein family members have been analyzed and certain ratios might correlate with response to BCL2 inhibitors (Roberts et al., 2012).

Therefore, detection of these and other cytogenetic abnormalities could have prognostic value and may guide therapeutic decisions.

6 STUDY OBJECTIVES AND ENDPOINTS

6.1 Study Objectives

6.1.1 Primary Objective

To determine the safety of MOR00208 combined with idelalisib or venetoclax

6.1.2 Secondary Objectives

1. To determine the quality of the response
2. To assess the potential immunogenicity of MOR00208
3. To assess the pharmacokinetic (PK) profile of MOR00208

6.1.3 Exploratory Objectives

- To assess minimal residual disease (MRD) in patients achieving a complete or partial response
- To explore putative predictive biomarkers
- To determine and correlate prognostic factors with efficacy parameters

6.2 Study Endpoints

6.2.1 Primary Endpoint

Incidence and severity of adverse events (AEs)

6.2.2 Secondary Endpoints

1. Overall response rate (ORR): defined for Cohort A as percentage of patients achieving a complete response (CR), a partial response (PR) or a partial response with lymphocytosis (PRL), and for Cohort B as percentage of patients achieving a CR or a PR
2. Anti-MOR00208 antibody formation
3. Pharmacokinetic analysis for MOR00208

6.2.3 Exploratory Endpoints

- Proportion of patients with MRD-negativity
- Absolute and percentage change from baseline in measurements for B-, T- and NK cell populations
- Analysis of exploratory and diagnostic biomarkers from blood (e.g., CD19 expression, BTK and PLC γ 2 mutational status, CD16 expression on NK cells, antibody dependent cell mediated cytotoxicity (ADCC) capacity, cytogenetics and mutational analysis).

7 INVESTIGATIONAL PLAN

7.1 Description of Study Design

This is a multicenter, two-cohort, open-label phase II study of MOR00208 combined with idelalisib (Cohort A) or venetoclax (Cohort B) for the treatment of adult patients with R/R CLL or R/R SLL pretreated with a BTK inhibitor as a single agent or as part of a combination therapy. Recruitment of a patient into Cohort A or B is at the discretion of the Investigator. A total of approximately 12 patients are planned to be enrolled in each cohort in Europe and the US. [Figure 1](#) illustrates the design of the main study.

The main study will include a safety run-in phase for each cohort enrolling 10- approximately 12 patients per combination treatment. MOR00208 will be administered at a dose of 12.0 mg/kg as intravenous (IV) infusion, idelalisib in Cohort A as 150 mg oral tablets twice daily and venetoclax in Cohort B as 400 mg oral tablets daily dose. To mitigate the risk for TLS treatment of patients with venetoclax will be initiated after an initial treatment with MOR00208 at 20 mg up from C1D8 for 7 days, followed by a weekly ramp-up dosing schedule to the recommended daily dose of 400 mg. The safety run-in phase will be concluded with an evaluation of the safety data of all treated patients once 10 patients completed at least one treatment cycle in Cohort A or at least 5 weeks of combination treatment in Cohort B. The first 3 patients in Cohort A will be dosed sequentially at least 48 hours apart. In Cohort B all 10- approximately 12 patients will be dosed sequentially, at least one week apart.

In Cohort A there will be two safety evaluations. After completion of the first cycle the safety data of the first three patients will be evaluated. This evaluation will be done by an IDMC composed of experts in the field of oncology and clinical biostatistics who have no other role in the study and do not have an affiliation with the Investigators or the sponsor. After the evaluation of the safety data from the first 3 patients for Cycle 1 of treatment and a positive recommendation from the IDMC the next 7- approximately 9 patients may be dosed in parallel. An additional IDMC review will take place after 10 patients completed at least 1 cycle of treatment.

In Cohort B the safety evaluation will be performed by an IDMC after the first 10 patients completed at least 5 weeks of combination treatment. The evaluation will be done by the IDMC as already described. Importantly, all patients in Cohort B, who participate in the safety run-in phase, will be hospitalized on the day of the first two dose escalations of venetoclax (C1D8 and C1D15).

The criteria for the evaluation of safety of the combination therapy will be defined by the IDMC and laid down in the IDMC Charter of the trial.

If safety evaluation results in a recommended dose reduction of idelalisib or venetoclax, the sponsor will reconsider dosing and amend the protocol accordingly.

During the study, MOR00208 will be administered as infusions 12.0 mg/kg in 28-day cycles. From Cycle 1 to 3, each cycle will consist of weekly infusions (on Day 1, Day 8, Day 15 and Day 22). In Cycle 1, an additional loading dose will be administered on Day 4. From Cycle 4 to 6, MOR00208 will be administered on a biweekly basis with infusions on Day 1 and Day 15

of each cycle. Thereafter, MOR00208 will be administered on Day 1 of each cycle starting with Cycle 7 Day 1.

Idealisib will be self-administered twice daily starting on Day 1 of each cycle. Venetoclax will be self-administered (except during hospitalization) starting from Cycle 1 Day 8 and on Day 1 of each cycle onwards. Treatment with idelalisib or venetoclax may be modified in a de-escalating fashion or discontinued based upon clinical and laboratory findings. In case idealisib or venetoclax treatment was stopped due to side effects suspected to be related to idealisib or venetoclax, the patient may continue MOR00208 treatment.

Progressive disease will require discontinuation of study medication.

[figure not shown]
Patients who benefit from treatment are allowed to continue MOR00208 treatment beyond Cycle 24 at Investigator's discretion. The total duration of the main study will be limited to a maximum of 5 years from first patient first visit or up to the timepoint of approximately 30 days after last patient received his last treatment, whichever comes first.

Patients completing the main study will be invited to participate in an optional biological marker sub-study as described in detail in Section 15.13 Appendix M.

MorphoSys AG Proprietary Information

nation

Figure 1: Study Design

*1 Additional loading dose of MOR00208 on Cycle 1 Day 4

*2 Weekly ramp up of Venetoclax starting on Cycle 1 Day 8 (C1D8: 20mg, C1D15: 50mg, C1D22:100mg, C2D1: 200mg). Venetoclax dosis 400mg up from Cycle 2 Day 8

Abbreviations: EOT=end of treatment; BTK=Bruton's tyrosine kinase; R/R CLL=relapsed or refractory chronic lymphocytic leukemia; R/R SLL=relapsed or refractory small lymphocytic lymphoma.

MorphoSys

